#### 4.5. Monitoring Plan

Monitoring will be performed by a trained person appointed by Philips to ensure compliance with the investigation plan, applicable national regulations and international standards, patient safety and data validity. The Sponsor may designate one or more individuals to monitor the progress of a clinical study. The Sponsor may also delegate the monitoring responsibilities to a third party. However, the Sponsor remains ultimately responsible for the conduct of the study. The Institution is responsible for the appropriate de-identification of subject data. The investigational site should provide access to the source data of the subjects.

All regulatory documents (e.g. MEC/IRB approval, contracts, etc.) will be reviewed for each actively participating center.

The first visit will occur as soon as possible after the first subject is enrolled at each study site. The monitoring schedule is based on the following considerations: enrollment rate, study compliance at the center, magnitude of data corrections required, study stage (e.g. start-up or follow-up), complexity of the investigation, IRB/MEC request, audit/inspection.

Critical data and processes will be monitored for this study prior to clinical report completion based on a risk based monitoring approach. Dependent on the risk a high or lower sample will be monitored.

The monitor will review critical clinical data that effect study endpoints. Data collection for reasons other than to support the protocol-defined endpoints will not be monitored.

A close-out visit for sites that have enrolled subjects will be conducted once the site has completed collecting data for the study.

Names of the monitor(s) can be found in Appendix II of this protocol. An update of this list can be provided to the site under separate cover.

Philips IGT Systems  Status: Approved	Post-Market Clinical Study Plan  CARO A multicenter observational cohort study	XCY610-130253 2018 Apr 06 Revision: 2.0 Page 16 of 23
--	---	--

## 5. STATISTICAL CONSIDERATIONS

Baseline patient characteristics and follow-up results will be summarized descriptively using frequencies and percentages or summary statistics like means and medians (including confidence intervals and interquartile ranges). Multiple imputation methods will be used to correct for missing data (Rubin, 1987).

### 5.1. Sample Size Justification

The total sample size for this study was calculated using the following formulas for Receiver Operating Characteristics Studies (Obuchowski, 2000):

$$n_D = \frac{[z_\alpha \sqrt{0.0792 \times (1 + 1/\kappa)} + z_\beta \sqrt{V(\theta)}]^2}{(\theta - 0.5)^2}$$

where  $V(\theta)$  is the variance function of  $\theta$ , given by:

$$V(\theta) = (0.0099 \times e^{-A^2/2}) \times ([5A^2 + 8] + [A^2 + 8]/\kappa)$$

i.e., the variance of  $\theta$  is equal to  $V(\theta)/n_D$ ;  $A = \Phi^{-1}(\theta) \times 1.414$ ;  $\Phi^{-1}$  is the inverse of the cumulative normal distribution function;  $\kappa$  is the ratio of the number of control patients ( $n_C$ ) to the number of diseased patients ( $n_D$ ) in the study sample (i.e.,  $\kappa = n_C/n_D$ );  $\theta$  is the conjectured area under the ROC curve (under the alternative hypothesis);  $z_\alpha$  is the upper  $\alpha$ th percentile of the standard normal distribution, where  $\alpha$  is the type I error rate (usually  $\alpha = 0.05$ ); and  $z_\beta$  is the upper  $\beta$ th percentile of the standard normal distribution, where  $\beta$  is the type II error rate (often  $\beta = 0.10$  or 0.20).

Assuming  $\kappa=0.25$  (i.e., 4 times as many occluded aneurysms than non-occluded aneurysms after 1 year), a fair AUC of 0.70, a type I error of 0.05 and a type II error rate of  $\leq 0.10$  (power  $\geq 0.90$ ), a total of 100 subjects should be included in the study. This total number of 100 subjects also accommodates the pre-planned explorative multivariate analysis allowing inclusion of 8 candidate predictors including AneurysmFlow (Peduz *et al.*, 1996). Allowing for an expected drop-out rate of 15% we aim to include a total of 120 patients into the study.

Any deviation from the planned analysis described below will be documented with justification in the final clinical end report.

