### 2.3 Clinical Experience

The clinical feasibility of the technique mentioned above using AneurysmFlow was previously evaluated using several clinical cases acquired during interventional procedures. This work compared Doppler ultrasound flow measurements with X-ray based flow measurements. The outcomes of these tests suggested that the use of the AneurysmFlow software is feasible during interventional procedures (Bonnefous *et al.*, 2012). Further validation of the technique was performed on a set of 22 clinical cases ([name] *et al.*, 2014). During that study, blood flow velocity in the internal carotid artery measured using AneurysmFlow was validated with Doppler sonography. Mean flow rates measured with the AneurysmFlow method significantly matched Doppler sonography measurements (slope regression coefficient,  $b=0.83 \pm 0.19$ ,  $P=0.05$ ). These initial results proved that blood flow velocity measurements can be measured reliably and accurately using the AneurysmFlow software.

The AneurysmFlow software has also been used for patients presenting with saccular unruptured IAs, to assess both flow modification after FDS implantation and correlation with aneurysm thrombosis. A metric has been defined, the Mean Aneurysm Flow Amplitude (MAFA) ratio, to measure the volumetric flow rate quotient before and after FDS implantation in the region of interest. Though preliminary, this MAFA ratio

Philips IGT Systems  Status: Approved	Post-Market Clinical Study Plan  CARO A multicenter observational cohort study	XCY610-130253 2018 Apr 06 Revision: 2.0 Page 11 of 23
--	---	--

index predicted thrombosis accurately with commercialized flow diverter stents. This was the first time blood flow could be appraised in in-vivo intracranial vessels during endovascular procedures ([name] *et al.*, 2013). Recently, a larger study conducted by the coordinating investigator confirmed these results (not yet published).

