## 2.1. Clinical study Justification

Previously published data has indicated that blood flow changes measured by the AneurysmFlow software predicted thrombosis accurately with commercialized Flow Diverting Stents (FDS). ([name] *et al.*, 2014) The purpose of the clinical study in this protocol is to investigate the ability of the intra-operative, intra-aneurysmal flow evaluation to assist with the treatment of intracranial aneurysms  $\geq 5\text{mm}$  using FDS.

The clinical hypothesis of this protocol to be tested is that by knowing the potential aneurysm occlusion rates by calculation of the MAFA ratio during a procedure, one might be able to adapt the therapeutic strategy intra-operatively to maximize the flow diverting effect for inducing complete aneurysm occlusions. Different strategies can be used to accelerate the aneurysm occlusion such as the addition of another stent layer or stent-assisted coiling with a jailed micro-catheter. Current treatment strategies are based on personal physician preferences or on subjective evaluation of aneurysm stagnation.

In this protocol, we propose to test a more quantitative assessment of the intra-aneurysmal flow, which may be able to support intra-operative clinical decisions which improve the occlusion rate of IA(s) after FDS treatment. Additionally, data collected in this proposed study will further expand the body of clinical knowledge concerning the relationship between blood flow metrics (including but not limited to the MAFA ratio) as determined by the AneurysmFlow software and clinical outcome in patients undergoing treatment for intracranial aneurysms with FDS.

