As shown in Figure 1, if a target aneurysm is treated with a FDS (or more than one) initially, and is then treated using another approach (such as coiling) then this target aneurysm can remain included as part of the study. However, if a target aneurysm is treated using a non-FDS approach initially (such as with coiling), followed by placement of an FDS or other approach, then the aneurysm will be excluded from the study.

Philips IGT Systems  Status: Approved	Post-Market Clinical Study Plan  CARO  A multicenter observational cohort study	XCY610-130253 2018 Apr 06 Revision: 2.0 Page 15 of 23
--	---	--

The MAFA ratio will be calculated after the placement of each FDS. For each FDS, this ratio will be determined with the flow information before any stents were placed and also with the flow information after each FDS was placed. The final MAFA ratio will be calculated using the flow information before any FDS devices were placed and using the flow information after the last FDS was placed. Clinical and imaging outcomes of a procedure will be assessed using a combination of the flow metrics calculated by the AneurysmFlow software available to the operator during interventional treatment in addition to information that is routinely acquired during FDS placement. This information acquired across the patient population in the study will also contribute to determine more precise MAFA ratio thresholds to improve prediction of complete aneurysm occlusion after FDS placement. This study will not make any recommendation on patient management or on treatment strategy. Also, this software will not disrupt standard-of-care workflow for the interventionalist.

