#### Experimental design

We will use logistic regression analysis to evaluate the univariate predictive association between the index test (i.e. the MAFA ratio) and complete aneurysm occlusion (i.e. complete occlusion yes/no) at 12 months (Moons *et al.*, 2012). All subjects with complete follow-up will be included in this analysis.

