#### Presentation format

The primary endpoint will be presented using an ROC curve including the c-statistic and confidence intervals.

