#### Experimental design

To determine the optimal threshold for the MAFA ratio, ROC analysis will be performed. The optimal threshold for clinical decision making will be determined using net-benefit analysis (Mallett *et al.*, 2012). Net benefit incorporates estimates of prevalence and misclassification costs, and it is clinically interpretable since it reflects changes in correct and incorrect diagnoses when a new diagnostic test is introduced.

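### Does the 5% error and 90% power in 5.1 fail because the plan fixes neither the direction of the MAFA ratio nor the confidence level?

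*Combined protocol and SAP*

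**What the plan says.** Section 5.1 sizes the study with a published ROC formula. The assumptions are "a fair AUC of 0.70, a type I error of 0.05 and a type II error rate of" at most 0.10, and four occluded aneurysms for each non-occluded one (kappa 0.25). The normal quantile for the type I error is defined there at alpha, not at half of alpha. The result is 100 subjects, raised to 120 for 15% drop-out.

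For the primary analysis, 5.4 (Experimental design) says: "We will use logistic regression analysis to evaluate the univariate predictive association between the index test", that is the MAFA ratio, and complete occlusion at 12 months. Under Presentation format it says: "The primary endpoint will be presented using an ROC curve including the c-statistic and confidence intervals". No level, null value or success criterion is given.

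On the marker itself, 2.3 describes the MAFA ratio as a metric "to measure the volumetric flow rate quotient before and after FDS implantation in the region of interest". Section 4.4 (Index Procedure and Discharge) says which acquisitions are used: "The final MAFA ratio will be calculated using the flow information before any FDS devices were placed" and the flow after the last one. Section 2.1 gives the mechanism, which is to "maximize the flow diverting effect for inducing complete aneurysm occlusions". The threshold analysis in 5.5.2 says: "To determine the optimal threshold for the MAFA ratio, ROC analysis will be performed".

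**The concern.** A one-sided test spends its whole 5% on one side, so it needs that side named beforehand. The readable text names neither the numerator and denominator of the ratio nor the direction that favours occlusion. A logistic regression takes the sign of its slope from the data. A c-statistic computed from fitted probabilities would therefore usually be turned to the side that looks better. If a one-sided 5% criterion were then applied, a useless marker would have two chances to pass instead of one. If the analyst instead used a two-sided 95% interval, the quoted 90% power would no longer apply.

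At stake would be the operating characteristics quoted for the primary endpoint. For a weak marker, the reported c-statistic would also be too high. The threshold in 5.5.2 needs the same information, because a cut-off has a favourable side.

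**Working it through.** **Inputs (5.1).** Theta 0.70 against 0.50; kappa 0.25; type I error 0.05; type II error 0.10; 100 evaluable; 120 enrolled; 15% drop-out.

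**1. Reproduce the plan's figure.**
- A = 1.414 × 0.5244 = 0.7415, so A² = 0.550.
- V = 0.0099 × exp(−0.275) × [(5 × 0.550 + 8) + (0.550 + 8)/0.25] = 0.338, with square root 0.581.
- Null term: sqrt(0.0792 × (1 + 1/0.25)) = sqrt(0.396) = 0.629.
- One-sided: n_D = (1.645 × 0.629 + 1.282 × 0.581)² / 0.20² = 79.2. Total = 79.2 × 1.25 = 99.0, which agrees with 100.
- Two-sided: with 1.960 in place of 1.645, n_D = 97.9 and the total is 122.3, which does not agree.

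The stated 100 is therefore a one-sided 5% calculation, correctly done.

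**2. Power at the planned size.** Power = Φ[(0.20 × sqrt(n_D) − z × 0.629) / 0.581], with n_D = N/1.25.

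| Evaluable N | n_D | One-sided 5% | Lower limit of two-sided 95% CI above 0.5 |
|---|---|---|---|
| 100 | 80 | 90.3% | 83.0% |
| 102 (120 × 0.85) | 81.6 | 90.8% | 83.8% |
| 120 | 96 | 94.4% | 89.4% |

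**3. Error when the marker is useless.** Doubling 5% for a sign chosen from the data gives 10%. The extra point is not a sign effect. The formula's null standard error at n_D = 80 is sqrt(0.396/80) = 0.0704, while the exact rank-based value is sqrt(101/(12 × 80 × 20)) = 0.0725. The one-sided error is then 1 − Φ(1.645 × 0.0704/0.0725) = 5.5%, and twice that is 11.1%.

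Simulation used 80 occluded and 20 non-occluded aneurysms, a normally distributed marker, the DeLong interval, and 30,000 to 40,000 runs per setting. At true AUC 0.50 it gives:

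| Criterion | Direction fixed | Sign taken from the fit |
|---|---|---|
| One-sided 5% | 5.5–5.7% | 11.1–11.3% |
| Lower limit of two-sided 95% CI above 0.5 | 3.0% | 6.1–6.3% |

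A log-normal ratio gives nearly the same results.

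**4. Effect on the reported c-statistic.**

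| True AUC | Mean c, direction fixed | Mean c, fitted sign |
|---|---|---|
| 0.50 | 0.500 | 0.557 |
| 0.55 | 0.550 | 0.570 |
| 0.60 | 0.600 | 0.605 |
| 0.70 | 0.700 | 0.700 |

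At 0.70 the fitted sign is wrong in 0.2% of runs. At 0.50, a reported c of 0.557 would carry a 95% interval of about 0.557 ± 1.960 × 0.0704, or 0.42 to 0.69 (null standard error). The reader would see that it includes 0.5. To exclude 0.5, c must reach 0.5 + 1.960 × 0.0704 = 0.638.

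**The case for a change.** The strongest case for a change is that 5.1 justifies the sample size by an error rate and a power against 0.5, which has meaning only if the interval is later compared with 0.5. On that reading, level and direction are left to be chosen after the data are seen. The freedom matters most for a weak marker, which is the case that a type I error rate is meant to cover. The remedy would cost a few words and no patients.

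Part of this stands. The label one-sided, the confidence level and the orientation of the ratio are not written in the readable text, though Figure 1 is not shown.

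The rest is weaker. That the data choose the sign is an inference: 5.4 makes the endpoint the c-statistic of the MAFA ratio, which can equally be computed from the raw ratio in a known direction. Nor does the analyst choose how the quotient is formed, because 4.4 has the software calculate it automatically. Section 2.3 reports that the ratio already predicted thrombosis in previous patients, and 4.4 seeks more precise thresholds, which suggests that earlier ones exist. With the mechanism in 2.1, an investigator who knows the device has what is needed to orient the ROC curve and the cut-off in 5.5.2.

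**Conclusion.** No change to the plan follows. The 5% and 90% in 5.1 are correct for the one-sided test that its own definition of the quantile describes, and no stated figure is wrong. An error of about 10 to 11% arises only if a one-sided 5% criterion is joined to a sign taken from the data. Power of 83% at 100 subjects (84% at 102, 89% at 120) arises only if rejection by a two-sided 95% interval is made the rule. The plan adopts neither, because its primary endpoint is an estimate with an interval and has no pass mark.

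What is left is a gap that analysts would fill sensibly. The usual 95% interval holds the null error at about 6% even with a fitted sign, and at the design AUC of 0.70 fixed and fitted orientation give the same c-statistic. These results assume an 80:20 split, an interval of DeLong type and a normal or log-normal marker. Anyone quoting power alongside a two-sided 95% interval should quote about 83%, but that is a matter for the report.

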In Step 3, after FDS deployment, a second DSA run with contrast agent will be acquired (i.e. injection rate  $\approx$ 1.5 to 2 cc/s) at the optimal C-arm viewing angle determined from the 3D-RA to qualitatively evaluate blood motion in the region of the aneurysm after deployment of the FDS. The C-arm angle and injection rate of this second DSA run (post FDS deployment) must be the same as the first DSA run (pre FDS deployment). The 2 DSA runs and the 3D-RA image volume will automatically be sent to the AneurysmFlow workstation right after they are acquired. If the FDS is ballooned after placement, the physician is asked to repeat Step 3 after ballooning.

In Step 4 a routine VasoCT scan, which is another 3D rotational x-ray C-arm scan, will then be performed with the x-ray C-arm in the neuro-interventional suite to evaluate the 3D apposition of the deployed FDS with respect the vessel wall.

The region of interest around the aneurysm and the corresponding arterial segment from which it has developed will be automatically segmented by the AneurysmFlow software, but manual controls are available in the software if modifications to the anatomical segment of interest are desired by the interventionalist. These modifications can be performed by an appropriately trained study member. The software will then automatically calculate the flow parameters of the aneurysm both before and after FDS deployment, along with the MAFA ratio.

For this study, the operator will have the choice of selecting which target aneurysms are amenable to FDS treatment. Patients that have single or multiple target aneurysms that are suitable for FDS treatment as a first treatment step would be acceptable for this study. Each target aneurysm in the patient will have a separate CRF sub-form to fill out. Additionally, each target aneurysm sub-form can be further divided into several FDS sub-forms to account for multiple flow diverters, if needed. To summarize, if the patient has more than one target aneurysm and/or needs more than one flow diverter per aneurysm, then a sub-form on the CRF will need to be filled out for each aneurysm and for each FDS used.

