### 5.2. General Consideration

The primary analysis of the prognostic value of the MAFA ratio for predicting full aneurysm occlusion 12 months after flow diverter placement will be performed including all subjects who underwent treatment. Baseline patient characteristics and follow-up results will be summarized descriptively using frequencies and percentages or summary statistics like means and medians (including confidence intervals and interquartile ranges). Multiple imputation methods will be used to correct for missing data (Rubin, 1987). All statistical analysis will be performed using R statistical software ([www.r-project.org](http://www.r-project.org))

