##### Experimental design

To explore which clinical variables have (independent) added value for predicting full aneurysm occlusion 6 and 12 months after flow diverter placement we use multivariate logistic regression methods. Candidate predictors (e.g., aneurysm location, size, medication) will be selected based on literature and expert opinion. Then, variable selection (i.e. backward selection using Akaike Information Criteria) will be used to determine the final set of predictors. Finally, internal validation and shrinkage of the model (i.e. using bootstrap methods) will be performed to correct for optimism. Information gained from this exploratory analysis can be used as valuable input for a future clinical prediction model for aneurysm occlusion.

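### The 100 subjects in Section 5.1 are said to support 8 candidate predictors, but the plan's own 4:1 ratio leaves about 20 non-occluded outcomes, or 2.5 per candidate

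*Combined protocol and SAP*

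**What the plan says.** Section 5.1 sizes the study with a formula for the area under the ROC curve. It assumes "4 times as many occluded aneurysms than non-occluded aneurysms after 1 year" (kappa = 0.25), an AUC of 0.70, type I error 0.05 and power of at least 0.90, and arrives at 100 subjects, raised to 120 for 15% drop-out. It then gives a second reason why 100 is enough: the number "accommodates the pre-planned explorative multivariate analysis allowing inclusion of 8 candidate predictors including AneurysmFlow". An events-per-variable study is cited, but Section 5.1 states no target number of events per variable and does not say which outcome class was counted.

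Section 5.6.2 describes the model. On the starting list it says: "Candidate predictors (e.g., aneurysm location, size, medication) will be selected based on literature and expert opinion". No final list is given. For reducing the list, the section states that "variable selection (i.e. backward selection using Akaike Information Criteria) will be used to determine the final set of predictors". As protection against overfitting, it adds that "internal validation and shrinkage of the model (i.e. using bootstrap methods) will be performed to correct for optimism". The endpoint is the selected model after shrinkage with its calibration and discrimination, and the intercept, coefficients, c-statistic and calibration slope are to be tabulated. The section adds that the information gained "can be used as valuable input for a future clinical prediction model for aneurysm occlusion".

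Two other statements bear on the count. Section 4.4 (Index Procedure and Discharge) accepts more than one aneurysm per subject: "Patients that have single or multiple target aneurysms that are suitable for FDS treatment". Section 5.2 says "Multiple imputation methods will be used to correct for missing data".

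**The concern.** Swapping the outcome coding of a logistic model reverses the signs of the coefficients and leaves the fit, standard errors and c-statistic unchanged. Calling occlusion the event therefore adds no information, and the scarcer outcome sets how many parameters the data can carry. Under the plan's own ratio the scarcer outcome is non-occlusion, with a quarter as many cases as the class on which the figure of 8 appears to rest.

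At stake is a reported exploratory endpoint. Selecting from 8 candidates with about 20 limiting outcomes gives unstable choices, coefficients that are too large and an apparent c-statistic that is too high. The plan offers this model as a basis for later prediction work, so a reader should know how thin that basis is.

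**Working it through.** **1. Reproduce the plan's total.** Inputs from Section 5.1: θ = 0.70, κ = 0.25, one-sided z_α = 1.645 (the section defines it as an upper percentile), z_β = 1.282.

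- A = Φ⁻¹(0.70) × 1.414 = 0.7415.
- V = 0.0099 × exp(−A²/2) × [(5A² + 8) + (A² + 8)/0.25] = 0.338.
- n_D = [1.645 × √(0.0792 × 5) + 1.282 × √0.338]² / 0.2² = 79.2, rounded up to 80 occluded.
- n_C = 0.25 × 80 = 20 non-occluded.
- Total = 80 + 20 = 100, as printed.

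**2. Limiting outcomes per candidate at 12 months,** with one target aneurysm per subject and one parameter per candidate:

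- 100 evaluable: 20/8 = 2.5.
- 120 less 15% = 102 evaluable: 20.4/8 = 2.55.
- All 120 evaluable: 24/8 = 3.0.
- Best case at 100 for any occlusion rate (50:50): 50/8 = 6.25.
- Larger class: 80/8 = 10. This is the probable origin of the 8, but it is an inference.

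**3. Effect of quantities the plan does not give** (ranges assumed):

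- Aneurysms per subject, 1.0 to 1.2: 20 to 24 non-occluded, so 2.5 to 3.0 per candidate before any allowance for clustering. Reaching 80 non-occluded at the same ratio needs 80/0.20 = 400 aneurysms, or four per subject.
- Location entered as 3 to 5 categories: 8 candidates become 9 to 11 parameters, so 20/9 = 2.2 down to 20/11 = 1.8 per parameter.
- Occlusion at 6 months, 60% to 80%: 40 to 20 non-occluded, so 5.0 to 2.5 per candidate in the 6-month model.

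**4. Consequence, by simulation.** Each data set has 100 subjects, 20 of them non-occluded, and 8 independent normal predictors. MAFA has AUC 0.70; the AUCs of the other seven are assumed. Backward AIC selection was applied, with 600 data sets per scenario and 40 bootstrap samples each, without multiple imputation. Runs that kept no predictor (9, 1 and 0) were left out.

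| | 7 others null | 3 at AUC 0.62, 4 null | all 7 at AUC 0.62 |
|---|---|---|---|
| Apparent c | 0.748 | 0.805 | 0.858 |
| True c | 0.659 | 0.716 | 0.767 |
| Corrected c, selection repeated | 0.661 | 0.729 | 0.792 |
| Optimism left, selection repeated | 0.002 | 0.013 | 0.024 |
| Corrected c, selection not repeated | 0.728 | 0.775 | 0.823 |
| Optimism left, selection not repeated | 0.068 | 0.059 | 0.055 |
| Calibration slope, raw | 0.56 | 0.59 | 0.58 |
| Slope after shrinkage, selection repeated | 0.89 | 0.92 | 0.91 |
| Slope after shrinkage, selection not repeated | 0.59 | 0.70 | 0.74 |

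Apparent minus true c is about 0.09 in each scenario. Some differences in the table are off by 0.001 through rounding. The slopes are medians in new data. The Monte Carlo standard error of the optimism left with selection repeated is 0.002 to 0.003. Some smaller repeat runs left 0.03 to 0.04 with selection repeated when candidates were informative, so that residual is best read as 0 to about 0.04.

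**The case against.** The plan prints no events-per-variable target and no division, so no stated threshold is missed, and 80/10 as the source of the 8 is a reconstruction. Eight is an upper allowance and the list is still open; with 4 candidates the figure would be 20/4 = 5. The analysis is exploratory and no primary or secondary endpoint rests on it. The plan commits to bootstrap validation and shrinkage, so the uncorrected 0.09 is not what it sets out to report. Whether selection is repeated in the bootstrap is a gap in specification, separate from the arithmetic. The simulation uses invented AUCs, independent predictors and no imputation.

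Most of this is fair, and it limits the weight of the point. The 2.5 applies if the full allowance is used. The amount to judge is what remains after correction. That remainder is small if selection is repeated and more than half of the 0.09 if it is not, and the plan leaves this open. The simulated values indicate size and do not forecast this study. None of it makes the statement in 5.1 correct: shrinkage moderates an overfitted model but does not supply limiting outcomes, and even an even split of 100 subjects gives only 6.25 per candidate.

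**Conclusion.** The concern holds. The calculation behind the 100 subjects supplies about 20 non-occluded outcomes at 12 months, so 8 candidates have 2.5 each (3.0 at most if all 120 are evaluable at the assumed ratio). The stated capacity is wrong as written. This rests on the plan's 4:1 ratio, one target aneurysm per subject and one parameter per candidate. Several aneurysms per subject would raise the figure slightly, and a multi-category location would lower it. The missing detail on the bootstrap is an omission, not an error, but it decides whether the reported c-statistic keeps 0 to about 0.04 or about 0.055 to 0.07 of optimism in the simulated settings. The point should be fixed. It does not touch the primary c-statistic or the total of 100.

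**What to change.** In Section 5.1, replace the capacity sentence with wording such as: *100 subjects give about 20 expected non-occluded outcomes at 12 months (assuming one target aneurysm per subject), i.e. 2.5 per candidate predictor for 8 candidates; the multivariable model is exploratory.* Alternatively, shorten the candidate list. In either case, count parameters and not variables for categorical candidates such as location, and count the 6-month model from its own smaller outcome class.

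In Section 5.6.2, add: *The AIC backward selection is repeated in every bootstrap sample; the optimism-corrected c-statistic and shrinkage factor come from these samples.* Because Section 5.2 plans multiple imputation, 5.6.2 should also say how selection and bootstrapping are combined across the imputed data sets.

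The cost is a few lines of text and a few minutes of computing, with no extra patients or data. The price is a less favourable stated capacity and a lower reported c-statistic. Unstable selection and some residual optimism will remain and should be acknowledged when the model is reported.
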